**Table 10-2: Study Visit Target Windows**

Study Visit	Target Window
Baseline	N/A
Device Trial Start	≤ 20 days after Baseline visit
Device Trial End	≤ 7 days after Device Trial Start
Device Implant	≤ 35 days after Device Trial End
Device Activation - Day 0	9-16 days after Device Implant; pending wound healing
1-Month	30 days ± 10 days after Day 0
3-Month	90 days ± 15 days after Day 0
6-Month	180 days ± 30 days after Day 0
12-Month	360 days ± 30 days after Day 0

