### **10.8.3 Device Trial End**

Subjects will be trialed per standard of care and within device labeling limits while enrolled into the study. Subjects will come in for the Device Trial End Visit within 7 days of the device trial start. At the Device Trial End Visit, if a subject has  $\geq 50\%$  improvement in overall pain with DTM-LE SCS programming, they will have their trial leads explanted and will proceed to implant. If a subject does not have  $\geq 50\%$  overall pain relief with DTM-LE SCS programming, they will be treated per standard of care and exited from the study. The outcome of the trial for those subjects that did not have a successful DTM-LE SCS trial will be recorded (success or failure). Trial lead explant must occur within 10 days of trial lead implant. Imaging may be performed to assess for lead migration if deemed necessary by the investigator.

The following information will be collected at the Device Trial End Visit:

- Percent Improvement in Overall Pain
- Programming parameters/device interrogation report(s) with initial and final settings
- Imaging (if performed)
- Changes to pain medications
- AEs/DDs

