## 7.10 Safety Evaluation

All device-related, therapy-related, and procedure-related adverse events and device deficiencies from the Device Trial Start Visit until study exit will be characterized.

Adverse events and device deficiencies will be coded and summarized using the most recent version of Medical Dictionary for Regulatory Affairs (MedDRA).

The adverse events will also be categorized by relationship to study device and/or therapy. Adverse events will be presented in summary tables displaying the number of serious events, the number of events, and the number and percentage of subjects with one or more events. A summary of all device or therapy related adverse events and of any deaths will also be provided. A narrative of each serious device- or therapy-related adverse event will be provided.

Device deficiencies will be presented in summary tables displaying the number of deficiencies, and the number and percentage of subjects with deficiencies.

Device exposure will be summarized by analysis set and is considered from the time the subject is first exposed to the neurostimulation system (at the beginning of the device trial) until the product is explanted, or the subject discontinues from or completes the study, if later. Amount of exposure will be summarized (in months) using descriptive statistics such as mean, standard deviation, minimum, and maximum.

Data from the Scheduled Follow Up CRF will be evaluated for subjects in the Completer Analysis Set to determine whether subjects were programmed within DTM-LE limits during the study. For subjects who

were programmed within DTM-LE limits, the months of DTM-LE exposure will be computed in the same way as above, with the Cut-off Date for DTM-LE extending until the date at which it was reprogrammed out of DTM-LE limits.

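### SAP 7.10 counts DTM-LE exposure without a break from device trial start, so it includes the 9–51 days (target windows) between trial lead removal and activation when no DTM-LE is delivered

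*SAP*

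**What the plan says.** SAP 7.10 defines two exposure measures.

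- **Device exposure** runs "from the time the subject is first exposed to the neurostimulation system (at the beginning of the device trial" until explant or, if later, until the subject leaves or completes the study. It is one continuous span, and because the later date governs, removal of the trial leads does not end it. Protocol 7.5 likewise treats exposure to the study product as one span from the start of the device trial.
- **DTM-LE exposure** applies to subjects in the Completer Analysis Set who were programmed within DTM-LE limits. For them "the months of DTM-LE exposure will be computed in the same way as above". The one stated change is to the end of the span: "with the Cut-off Date for DTM-LE extending until the date at which it was reprogrammed out of DTM-LE limits". The start date is not reset and no interval is subtracted. Whether a subject was within limits is judged as follows: "Data from the Scheduled Follow Up CRF will be evaluated for subjects in the Completer Analysis Set".

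The protocol describes what happens inside that span. Under 10.8.3, subjects with a successful trial are treated thus: "they will have their trial leads explanted and will proceed to implant". The same section adds a time limit: "Trial lead explant must occur within 10 days of trial lead implant". Table 10-2 sets implant at no more than "35 days after Device Trial End" and activation at "9-16 days after Device Implant; pending wound healing". Section 10.9 has staff confirm after implant that stimulation is off. Section 10.10 turns it on at activation (Day 0) and postpones that visit if the wound has not healed. SAP section 5 gives about 9–12 days for implant to activation, which differs from the protocol's 9–16.

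**The concern.** A measure named DTM-LE exposure should count time on DTM-LE. Under the written rule it also counts two intervals in which that therapy cannot be delivered: from trial lead removal to implant, when no leads are in place, and from implant to activation, when the stimulator is off. Every subject for whom the measure is computed has at least the second interval, so the error always runs upwards.

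What is at stake is the accuracy of the only DTM-LE duration in the visible SAP, in a study whose purpose is to evaluate DTM-LE. The added days do not depend on how long the subject stays within limits, so the proportional error is largest for subjects reprogrammed out of limits early. Those are the subjects this calculation is meant to separate from the rest.

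**Working it through.** The documents give no figure for this interval or for expected DTM-LE exposure, so there is no stated number to reproduce.

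**Inputs**

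- Trial length T: at most 7 days (Table 10-2). Assumed to be 7, with leads removed at the Trial End Visit.
- Gap g from trial lead removal to implant: 0–35 days (Table 10-2, under the same assumption).
- Off period f from implant to activation: 9–16 days (Table 10-2), or 9–12 days (SAP section 5).
- D: days from activation (Day 0) until the subject leaves DTM-LE limits. Illustrated at 90, 180 and 360, the target days of the 3-, 6- and 12-Month visits.
- One month = 30.4375 days.

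**Formulas**

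- Counted under SAP 7.10 = T + g + f + D
- Span with DTM-LE programmed and available = T + D
- Overcount = g + f

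**Overcount in days**

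- Protocol windows: 0 + 9 = 9 to 35 + 16 = 51 days, or 9/30.4375 = 0.30 to 51/30.4375 = 1.68 months.
- SAP section 5 interval: 0 + 9 = 9 to 35 + 12 = 47 days.
- Middle of both protocol windows (assumption): 17.5 + 12.5 = 30 days.

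**Overcount relative to the DTM-LE span (T = 7)**

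| Within limits until | T + D | Counted, protocol windows | Overcount, protocol windows | Mid-window | Maximum with SAP's 9–12 days |
|---|---|---|---|---|---|
| Day 360 | 367 | 376–418 | 9/367 = 2.5% to 51/367 = 13.9% | 30/367 = 8.2% | 47/367 = 12.8% |
| Day 180 | 187 | 196–238 | 9/187 = 4.8% to 51/187 = 27.3% | 30/187 = 16.0% | 47/187 = 25.1% |
| Day 90 | 97 | 106–148 | 9/97 = 9.3% to 51/97 = 52.6% | 30/97 = 30.9% | 47/97 = 48.5% |

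**Sensitivity to the assumptions**

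- Trial leads left in and on to Day 10, the latest removal day, after a Trial End Visit on Day 7: g becomes 0–32, so the overcount is 9 to 32 + 16 = 48 days. At Day 360 this is 9/370 = 2.4% to 48/370 = 13.0%; at Day 90, 9/100 = 9.0% to 48/100 = 48.0%.
- The 51 days is a sum of target windows, not a cap. Each day that activation slips past 16 days after implant adds one day. Seven days late gives 51 + 7 = 58 days: 58/367 = 15.8% at Day 360 and 58/97 = 59.8% at Day 90.

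**The case against.** The strongest case against acting is that nothing depends on this number. It is a descriptive summary, it is neither a primary nor a secondary endpoint, and the visible SAP uses no adverse event rate per month of exposure. That is correct, and it limits the importance of the point.

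A second argument is that a continuous calendar span is the documents' own convention: device exposure also contains the days between trial lead removal and implant. But protocol 7.5 defines exposure to the study product, not to DTM-LE. The SAP chose to create a separate therapy measure, and the convention does not fit it.

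Third, T + D is not exact delivered time either, because the therapy cycles on and off and subjects can switch the device off. Cycling is part of DTM-LE, so it is not an error. Switching off by the subject remains uncounted, so the corrected figure is a closer approximation, not an exact one.

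Fourth, the largest percentages need both windows at their maximum and an early departure from limits, and the documents do not say how often subjects leave limits. That stands. The mid-window figure for a subject within limits to Day 360 is about 8%, and no effect on the group mean can be given.

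Fifth, the instruction to compute in the same way could be read as referring only to the summary statistics, and the analysis-set section, SAP 7.1.3, is not visible. The sentence nevertheless says how the months are computed and adjusts only the end, and 7.10 as released shows no other start or interruption rule. If another rule was intended, it should be stated.

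**Conclusion.** The concern holds. Followed exactly, SAP 7.10 gives a DTM-LE exposure that is too long for every subject for whom it is computed: by 9–51 days on the protocol's target windows, or 9–47 days on the SAP's activation interval. With a 7-day trial and leads removed at the Trial End Visit, that is 2% to 14% for a subject within limits to Day 360, 5% to 27% at Day 180 and 9% to 53% at Day 90. The day counts rest on the target windows and are exceeded if activation is postponed; the percentages also rest on the assumed trial length.

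The effect is confined to the DTM-LE exposure summary. The VAS analyses, adverse event counts and percentages, and device exposure are unaffected. It is worth correcting because the error is always in one direction and the remedy is small.

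A lesser point is one of detail. Status within limits is taken from the scheduled follow-up form, while protocol 10.13 allows reprogramming at unscheduled visits. The SAP does not say how the out-of-limits date is then established.

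**What to change.** In SAP 7.10, replace the instruction to compute DTM-LE months like device exposure with an explicit sum: (device trial start to trial lead removal, or to the Trial End Visit if the removal date is not recorded) + (device activation to the first of out-of-limits reprogramming, explant or study exit).

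Also:

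- Take the out-of-limits date from the follow-up form and the available interrogation reports from scheduled and unscheduled visits. Where the date is known only to an interval, say so.
- State whether time counts again if a subject leaves limits and later returns. The sum above stops at the first departure.
- Leave device exposure as it is. It agrees with protocol 7.5, and the change does not contradict that section.
- Reconcile the implant-to-activation interval between SAP section 5 and protocol Table 10-2.
- Optionally, report DTM-LE exposure for all activated subjects as well.

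The core change is one sentence in the SAP and needs no protocol amendment. It has three costs. Reported DTM-LE months become 0.3–1.7 shorter per subject on target windows. The trial lead removal date is not among the items listed for the Trial End Visit in protocol 10.8.3, so the visit date may have to stand in. And unscheduled interrogation reports, which are transferred as PDF files, will need some review.

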## 7.11 Changes to Planned Analysis

Any deviations from this SAP will be described in the final study report, as appropriate.

## 8. Validation Requirements

Statistical programming code that affects the result of the main analysis (e.g., not including sensitivity or supporting analyses) for the primary objective shall be validated using Level I validation. Programming code that affects the result of the main analysis for the secondary objective shall be validated using at least Level II validation. In addition, those main statistical analyses that are planned for publication and have not been previously validated should be validated using at least Level II validation. The CIP deviation summary shall be validated using at least Level III validation and the high-level adverse event summary shall be validated using at least Level II validation. Additional measures where a confidence interval has been generated may need to be validated using at least Level II validation.

## **10. Appendices**

---
